#### 4.6. Pharmacodynamic and Other Biomarker Variables

##### Serum Antibodies

- Allergen-specific IgE levels (cat hair, Fel d 1) at screening visit 1 (V1) and baseline.
- Allergen-specific IgE levels (Fel d 2, Fel d 4, Fel d 7, and other common allergens) at screening and baseline to assess sensitization status and to evaluate the relationship between response to REGN1908-1909 and poly/mono-sensitization ([van Ree 1999](#)).
- Allergen-specific IgE levels (cat hair, Fel d 1, Fel d 2, Fel d 4, Fel d 7, and other common allergens on days 8, 29, 57, and 85 using blood samples collected prior to the Controlled Cat Allergen Challenge in the EEU
- Additional subclass of serum antibodies (eg, IgG4 against Fel d 1, 2, 4, 7) may be measured at screening, baseline, and on days 8, 29, 57, and 85 using blood samples collected prior to the allergen challenge

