**Figure 2: Study Flow Diagram Schema 2**

Before entry into the cat allergen exposure unit, prohibited medications are withheld (See Prohibited Medications Section [7.8.1](#)), and patients receive a physical examination; chest, nasal, and ocular symptoms, as well as pulmonary function, will be evaluated and recorded. The challenge will not proceed if patients have a TNSS greater than 4, an asthma control test (ACT) score  $< 20$  at any of the screening visits, or FEV1 of less than 70% of predicted value. Patients may leave the exposure unit at any time. Patients wear a disposable suit to protect them from allergen inside the EEU and to avoid contaminating the EEU with other allergens brought in from their clothing, which could interfere with the cat allergen studied.

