**7.8.1. Prohibited Medications**

1. Use of these concomitant medications within the following time period is preceding any screening visit or any EEU visit:

(NOTE: Patients may be rescheduled 1 time for the screening visit or EEU visit after the time period for taking these concomitant medications has passed.)

- a. Topical or systemic first generation H1 antihistamines (5 days)
- b. Topical or systemic second generation H1 blockers (7 days)
- c. Systemic anti-H2 (8 days)
- d. Atemizole (6 weeks)
- e. Cromoglycates, leukotriene modifiers (7 days)
- f. Systemic steroid treatment (8 weeks prior to screening and during the study)

(NOTE: systemic steroid treatment is allowed if clinically indicated for a LAR treatment after exposure to cat allergen in the EEU.)

- g. Topical steroids (48 hours)
- h. Short-acting  $\beta$ 2 agonists (8 hours)
- i. Long-acting  $\beta$ 2 agonists (eg, salmeterol) (36 hours)
- j. Ultra-long-acting  $\beta$ 2 agonists (eg, indacaterol, vilanterol, olodaterol) (48 hours)
- k. Anticholinergics eg, Ipratropium (Atrovent 40  $\mu$ g) (12 hours)
- l. Long-acting anti-muscarinic agents (7 days)
- m. Methylxanthines (eg, oral theophylline) (24 hours)
- n. Intramuscular corticosteroids (3 months prior to screening and during the study)
- o. Systemic or topical calcineurin inhibitors (14 days prior to screening and during the study)
- p. Tricyclic antidepressants/antipsychotics (14 days)
- q. Topical decongestants (72 hours)
- r. Caffeine-containing drinks or products (8 hours of EEU visits only)

2. History of SIT with cat allergen or vaccines against cat allergy within 5 years of screening
3. SIT with any allergen within 6 months of screening
4. Beta-blockers during the study period
5. Immunomodulatory therapy, anti-IgE, or other biological, agent-based antagonist therapy is not allowed in the 6 months prior to baseline (eg, cyclosporine) or during the study
6. Change in prescription medications within 4 weeks before screening
7. Aspirin and any nonsteroidal anti-inflammatory drug

NOTE: paracetamol is allowed to be used for occasional pain relief.

8. Active treatment for respiratory infections (antiviral, antifungals, or antibiotics) within 4 weeks prior to screening or EEU

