## **10.3. Analysis Sets**

### **10.3.1. Efficacy Analysis Sets**

The FAS includes all randomized patients who received any study drug; it is based on the treatment allocated (as randomized). Efficacy endpoints will be analyzed using the FAS.

The per protocol analysis set (PPS) includes all patients in the FAS except for those who are excluded because of efficacy-related major protocol violations. Final determination of the PPS will be made prior to the database lock and will be outlined in the SAP.

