#### **10.4.3.2. Secondary Efficacy Analysis**

The time to EAR for Cat Allergen Challenges on days 29, 57, and 85 will be evaluated in a similar way to the primary analysis. The time course of asthma response comprising EAR and LAR will be visualized and summarized. Methods for handling missing data in the case that a patient does not complete 1 or more of the Cat Allergen Challenges will be addressed in the SAP.

The AUC of percentage change from baseline FEV1 during the Controlled Cat Allergen Challenge will be analyzed by mixed-effect model repeated measures (MMRM) with the treatment, time, treatment-by-time interaction, and day of challenge as factors and baseline FEV1 as a continuous covariate. An unstructured covariance structure will be utilized; if the model does not converge, an autoregressive structure will be employed. Between-group estimates and nominal p values will be reported for Controlled Cat Allergen Challenges on days 8, 29, 57, and 85. The AUC will be a time-adjusted-based duration of exposure to account for patients exiting the EEU at different times. Missing data from Controlled Cat Allergen Challenges on days 8, 29, 57, or 85 will be accounted for via MMRM. The AUC of percent change in TNSS and TOSS and change and percent change in cat allergen exposure from the baseline Cat Allergen Challenge, will be analyzed in a similar manner.

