3.1. The Full Analysis Set (FAS)

FAS includes all randomized subjects who receive any investigational product and have completed the Day 8 Cat Allergen Challenge. Efficacy analyses will be based on the treatment allocated by the IVRS at randomization (as randomized).

FAS is the primary analysis set for efficacy endpoints.

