5.6.2. Analysis of Secondary Efficacy Variables

The time to EAR for Cat Allergen Challenges on days 29, 57, and 85 will be evaluated in a similar way to the primary analysis.

The change and percent change from the Baseline Controlled Cat Allergen Challenge in AUC of FEV1 (L) during the Controlled Cat Allergen exposure will be calculated and analyzed by mixed-effect model repeated measures (MMRM) with the treatment, visit, and treatment-by-visit interaction as factors and the AUC of FEV1 during the baseline Controlled Cat Allergen Challenge, time to EAR during the baseline controlled cat allergen challenge, and allergen concentration in the EEU for each visit as continuous covariates. The primary method for the calculation of the AUC is described in Section 6.2, where last observation carried forward (LOCF) is used to calculate the AUC from 0 to 2 hours. An unstructured covariance structure will be utilized; if the model does not converge, an autoregressive structure will be employed. Between-group estimates and nominal p values will be reported for Controlled Cat Allergen Challenges on days 8, 29, 57, and 85. Missing data from Controlled Cat Allergen Challenges on days 8, 29, 57, or 85 will be accounted for via MMRM. The change from the Baseline Challenge in AUC of TNSS and TOSS will be analyzed in a similar manner.

The change and percent change in cat allergen quantity (tolerated exposure) from the baseline Cat Allergen Challenge, will also be analyzed using a similar MMRM model with the treatment, visit, and treatment by-visit interaction as factors and the cat allergen quantity tolerated in the baseline Controlled Cat Allergen Challenge as a covariate.

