6.3. Data Handling Convention for Missing Data

Rules for handling missing data for primary and secondary efficacy variables are described in Section 4.5.1 and Section 4.5.2.

For categorical variables, patients with missing data are not included in calculations of percentages unless otherwise specified. When relevant, the number of patients with missing data is presented.

To determine whether a medication is prior or concomitant, the missing medication start date is estimated as early as possible up to randomization date, and the missing medication end date is

estimated as late as possible. If the medication start date is missing, the onset day will not be imputed in medication listings.

If a baseline value is missing for an efficacy endpoint, the patient will be excluded from analyses involving a change or percent change from baseline.

Adverse event

If the intensity of a TEAE is missing, it will be classified as “severe” in the frequency tables by intensity of TEAEs. If the assessment of relationship of a TEAE to the investigational product is missing, it will be classified as related to the investigational product.

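### The SAP's full analysis set requires a completed Day 8 challenge, which the protocol does not, so a dosed patient who misses only Day 8 is left out of the Day 29 to 85 efficacy and biomarker analyses

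*SAP*

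**What the plan says.** The two documents define the full analysis set differently. Protocol 10.3.1: "The FAS includes all randomized patients who received any study drug; it is based on the treatment allocated (as randomized"). SAP 3.1: "FAS includes all randomized subjects who receive any investigational product and have completed the Day 8 Cat Allergen Challenge". The protocol synopsis is looser than either and describes the FAS only as randomised patients. SAP 1.2.3, which lists what changed from SAP version 1, does not mention the FAS.

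SAP 3.1 makes this set primary for the efficacy endpoints. The table in SAP 10.1 assigns it to time to EAR at Days 29, 57 and 85 and to every MMRM endpoint. SAP 5.10 uses it for all biomarker analyses and SAP 5.1 for the baseline table. Under SAP 3.2 the per-protocol set is drawn from within the FAS.

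On missed challenges, Protocol 10.4.3.2 says that the missing-data methods "in the case that a patient does not complete 1 or more of the Cat Allergen Challenges will be addressed in the SAP". SAP 6.3 responds: "Rules for handling missing data for primary and secondary efficacy variables are described in Section 4.5.1 and Section 4.5.2". SAP 5.6.2, for the AUC endpoints, says: "Missing data from Controlled Cat Allergen Challenges on days 8, 29, 57, or 85 will be accounted for via MMRM".

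**The concern.** Whether a patient has completed the Day 8 challenge is known only about a week after dosing. Making it a condition of FAS membership lets a post-randomisation event decide who is analysed, at later visits as well as at Day 8.

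The protocol foresees that a challenge may not take place. Section 5.1 sets conditions on the day: "The challenge will not proceed if patients have a TNSS greater than 4", with a further condition on FEV1. A dosed patient held back on Day 8 and not rescheduled may attend Days 29, 57 and 85 and give valid data there. Under SAP 3.1 the FAS-based analyses use none of it. The same holds for allergen-specific IgE on those days, which Protocol 4.6 measures "using blood samples collected prior to the Controlled Cat Allergen Challenge in the EEU". Patients who opt out of all challenges but stay in the study (Protocol 7.3.2) have no later EAR or AUC data to lose, but their remaining biomarker and skin-prick results also fall outside the set.

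At stake are valid later-visit data, agreement between protocol and SAP on the primary efficacy population, and a missing-data rule that cannot do what it says for Day 8.

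**Working it through.** **1. Follow one patient through the plan.** Take a patient who is randomised and dosed, has no Day 8 challenge, and attends Days 29, 57 and 85.

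| Analysis | Set used | Protocol 10.3.1 FAS | SAP 3.1 FAS |
|---|---|---|---|
| Day 8 time to EAR | FAS, PPS | no Day 8 time to analyse | out |
| Days 29, 57, 85 time to EAR | FAS, PPS | in | out |
| MMRM endpoints | FAS | in, Day 8 missing | out |
| Biomarkers (SAP 5.10) | FAS | in | out |
| Baseline table (SAP 5.1) | FAS | in | out |
| Safety (SAP 3.3) | SAF | in | in |

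**2. Test the missing-data rules against this patient.** SAP 4.5.1 contains endpoint and 4-hour censoring rules. SAP 4.5.2 contains endpoint definitions, symptom scales and spirometry procedure. Neither has a rule for a challenge that did not happen, so the SAP 6.3 reference leads nowhere on this point. The MMRM sentence in SAP 5.6.2 names Day 8, but SAP 3.1 removes the patient before any model is fitted. For Day 8 the sentence keeps a meaning only for a FAS member whose Day 8 value cannot be computed.

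**3. Check that the primary power statement is not affected.** Inputs from SAP 2.2: medians 58 and 132 minutes, HR 0.44, one-sided 0.05, 60 patients less 8 dropouts = 52. Maximum exposure is 240 minutes (SAP 4.5.1). With exponential times:

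- Events = 26 × [(1 − 0.5^(240/58)) + (1 − 0.5^(240/132))] ≈ 43.2.
- Schoenfeld power = Φ(√43.2 × |ln 0.44|/2 − 1.645) ≈ 85.4%.
- Simulated log-rank power with 26 per arm is 86.0% with continuous times and 84.7% on the 10-minute spirometry grid.

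The stated 84% is reproduced within 2 points. It already allows for 8 losses, and the FAS clause does not alter it.

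**4. Size at a later visit.** The plan states 88% power for the FEV1 AUC with 60 patients, one-sided 0.05, and gives no standard deviation. The 88% is therefore taken as given and inverted by a two-sample normal approximation:

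- Standardised effect = (1.645 + 1.175) × √(2/30) = 0.728.

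Let k be the number of dosed patients who miss only Day 8. The documents give no value, so 1, 2 and 4 are assumptions.

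- Rise in standard error = √(60/(60 − k)) − 1.
- Power = Φ(2.820 × √((60 − k)/60) − 1.645).
- Share of the 60 × 3 = 180 planned later challenges lost, at most 3k/180.

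| k | SE rise | Power | Later challenges lost, at most |
|---|---|---|---|
| 0 | 0 | 88.0% | 0 |
| 1 | 0.8% | 87.5% | 3 (1.7%) |
| 2 | 1.7% | 87.0% | 6 (3.3%) |
| 4 | 3.5% | 86.0% | 12 (6.7%) |

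This assumes equal information per patient, balanced arms, no other losses, and the planned effect persisting at later visits.

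**The case against.** The strongest reply is that the clause may never matter. No rate of missed Day 8 challenges is given. A challenge that is held back is not necessarily lost: Protocol 7.8.1 allows one rescheduling of an EEU visit for the washout medicines in its first item, and Protocol 10.6 keeps out-of-window assessments under the visit recorded on the case report form, so a late Day 8 challenge might still count. Even with four such patients the loss of power is 2 points, in analyses with nominal p values and no multiplicity control. Because SAP 5.5 tabulates both FAS and SAF, the number of dosed patients excluded would largely be visible. All of this stands, and it limits the size of the point.

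It is also said that Protocol section 10 and SAP section 1 allow the SAP to be revised, and that the protocol is not uniform, since the synopsis omits dosing. Both are true. But neither protocol definition has a Day 8 condition, and a general permission to revise gives no reason for this change.

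Three stronger readings may tempt a reader, and the documents do not support them:

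- **The primary result is compromised.** A patient with no Day 8 challenge has no Day 8 time to EAR under either definition. A problem would arise only if completion were read to exclude those who leave early, and SAP 5.6.1 explicitly keeps and censors patients who leave for reasons unrelated to symptoms.
- **Later comparisons are biased.** Exclusion after randomisation makes bias possible, but nothing in the documents shows that missing Day 8 would differ by arm.
- **Losses at Day 8 are likely because of the rule on "Active treatment for respiratory infections (antiviral, antifungals, or antibiotics) within 4 weeks prior to screening or EEU".** Day 8 has a window of 2 days either side, so a course ending on Days 7 to 10 may follow a challenge already done. A course running on Day 1 should have stopped randomisation, since exclusion criterion 12 bars prohibited treatments and eligibility is rechecked at visit 5.

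**Conclusion.** The point holds as a discrepancy between SAP and protocol with a definite consequence: SAP 3.1 adds an unexplained post-randomisation condition to the FAS, and any dosed patient who misses only Day 8 loses all later FAS-based efficacy and biomarker data. It also contradicts the use of MMRM for missing Day 8 challenges in SAP 5.6.2. Set membership follows from the text and needs no assumption.

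The size does need one. The number of patients is unknown and may be zero. At an assumed 1 to 4, the later-visit standard error rises by about 0.8% to 3.5% and 88% power becomes about 87.5% to 86.0%. The Day 8 Cox analysis is little affected, and the analyses that lose data are secondary or exploratory. This ranks between a minor point and one that should be fixed. What favours acting is that the correction is cheap and removes an avoidable exclusion.

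**What to change.** - **SAP 3.1:** delete the Day 8 completion condition and restore the Protocol 10.3.1 definition (randomised and dosed, analysed as randomised).
- **Day 8 time to EAR:** analyse every FAS patient who entered the Day 8 challenge, with early leavers handled as SAP 5.6.1 already provides. This also settles what completion was meant to cover.
- **Days 29 to 85, the MMRMs and the biomarkers:** analyse all FAS patients with data at the relevant visit.
- **SAP 6.3:** replace the reference to sections 4.5.1 and 4.5.2, for missed challenges, with this rule.
- **SAP 5.5:** report by arm the dosed patients without a Day 8 challenge, with reasons.

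The cost is a few sentences of SAP text and one disposition line. No new data and no change to trial conduct are needed. SAP section 1 requires revisions to rest on blinded review and the final plan to precede code breaking, so the change belongs before any unblinding, including that for the first-step analysis.

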3.2. The Per Protocol Set (PPS)

PPS includes all subjects in the FAS except for those who may relate to efficacy analysis and who are excluded because of major protocol violations . A major protocol violation is one that may affect the interpretation of study efficacy results. Final determinations of the PPS will be made before data base lock.

Major protocol violation:

The criteria of major protocol deviation are defined as following:

- Had not received study treatment
- Had any major violations of entry criteria
- Had not received treatment as randomized
- Had taken any prohibited medication during the double-blind phase

3.3. The Safety Analysis Set (SAF)

SAF includes all subjects who receive any investigational product and be analyzed as treated. Treatment compliance/administration and all clinical safety variables will be analyzed using the SAF. No missing data will be imputed for safety analyses.

3.4. The Pharmacokinetic Analysis Set (PKAS)

The PKAS includes all treated patients who received any study drug and had at least 1 non-missing blood sample for drug concentration following a single dose of REGN1908-1909. Patients will be analyzed according to the treatment actually received.

3.5. The Anti-Drug Antibody (ADA) Analysis Set

The anti-drug antibody (ADA) analysis set will consist of all patients who received any study drug and who had at least 1 non-missing ADA result in the anti-REGN1908 or anti-REGN1909

assay after a single dose of the study drug. Patients will be analyzed according to the treatment actually received.

4. ANALYSIS VARIABLES

4.1. Demographic and Baseline Characteristics

The following demographic variables will be summarized:

- Age at screening (year)
- Age range if needed
- Sex (Male, Female)
- Race (American Indian/Alaskan Native, Asian, Black/African American, Native Hawaiian/Other Pacific Islander, White and Other)
- Ethnicity (Hispanic/Latino)
- Baseline Weight (kg)
- Baseline Height (cm)
- Baseline Body mass index (BMI) calculated from weight and height (kg/m²)

The following baseline characteristics will be summarized:

- Minute ventilation (L/min)
- FEV1 (L)
- Baseline challenge FEV1 AUC
- Baseline challenge TNSS AUC
- Baseline challenge TOSS AUC
- Screening skin prick test for cat allergen (mm)
- Skin prick test for other common allergens (mm)
- Skin Prick Test with Serial Allergen Titration, measured by AUC of the wheal sizes (diameter) over log-transformed allergen concentrations
- Baseline serum total IgE
- Baseline serum cat hair sIgE
- Baseline serum Fel d 1 sIgE
- Baseline serum Fel d 2 sIgE
- Baseline serum Fel d 4 sIgE
- Baseline serum Fel d 7 sIgE

4.2. Medical History

Medical history will be coded to a Preferred Term (PT) and associated primary System Organ Class (SOC) according to the latest available version of Medical Dictionary for Regulatory Activities (MedDRA®).

4.3. Pre-Treatment / Concomitant Medication

Medications/Procedures will be recorded from the day of informed consent until the end-of-study (EOS) visit. This includes medications that were started before the study and are ongoing during the study.

Medications will be coded to the ATC level 2 (therapeutic main group) and ATC level 4 (chemical/therapeutic subgroup), according to the latest available version of WHO Drug Dictionary (WHODD). Patients will be counted once in all ATC categories linked to the medication.

Pre-treatment medications/procedures: medications taken or procedures performed prior to administration of the study drug.

Concomitant medications/procedures: medications taken or procedures performed following the dose of study drug through the EOS visit, with the exception of rescue treatment kit medications taken at home within 24 hours from the EEU exposure.

4.4. Rescue Medication/or Prohibited Medication During Study

The use of the following concomitant medications is not permitted during the study:

1. Use of these concomitant medications within the following time period preceding any screening visit or any EEU visit:

(NOTE: Patients may be rescheduled 1 time for the screening visit or EEU visit after the time period for taking these concomitant medications has passed.)

- a. Topical or systemic first generation H1 antihistamines (5 days)
- b. Topical or systemic second generation H1 blockers (7 days)
- c. Systemic anti-H2 (8 days)
- d. Atemizole (6 weeks)
- e. Cromoglycates, leukotriene modifiers (7 days)
- f. Systemic steroid treatment (8 weeks prior to screening and during the study)

(NOTE: systemic steroid treatment is allowed if clinically indicated for a LAR treatment after exposure to cat allergen in the EEU.)

- g. Topical steroids (48 hours)
- h. Short-acting β 2 agonists (8 hours)
- i. Long-acting β 2 agonists (eg, salmeterol) (36 hours)
- j. Ultra-long-acting β 2 agonists (eg, indacaterol, vilanterol, olodaterol) (48 hours)
- k. Anticholinergics eg, Ipratropium (Atrovent 40 μ g) (12 hours)
- l. Long-acting anti-muscarinic agents (7 days)
- m. Methylxanthynes (eg, oral theophylline) (24 hours)
- n. Intramuscular corticosteroids (3 months prior to screening and during the study)
- o. Systemic or topical calcineurin inhibitors (14 days prior to screening and during the study)
- p. Tricyclic antidepressants/antipsychotics (14 days)
- q. Topical decongestants (72 hours)

- r. Caffeine-containing drinks or products (8 hours of EEU visits only)
2. History of systemic immunotherapy (SIT) with cat allergen or vaccines against cat allergy within 5 years of screening
3. SIT with any allergen within 6 months of screening
4. Beta-blockers during the study period
5. Immunomodulatory therapy, anti-IgE, or other biological, agent-based antagonist therapy (eg, cyclosporine) is not allowed in the 6 months prior to baseline or during the study
6. Change in prescription medications within 4 weeks before screening
7. Aspirin and any nonsteroidal anti-inflammatory drug

NOTE: paracetamol is allowed to be used for occasional pain relief.

8. Active treatment for respiratory infections (antiviral, antifungals, or antibiotics) within 4 weeks prior to screening or EEU

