#### **Early Asthmatic Response (EAR) and Late Asthmatic Response (LAR)**

During a session in the EEU, an EAR is expected to be mild or moderate. As soon as the patient has a drop in FEV1 of 20% and/or asthma symptoms, the patient will be removed from the EEU and will be treated with short-acting  $\beta$ 2 agonist every 20 minutes for 1 hour if necessary. Patients will stay under supervision in the observation room during 6 hours after leaving the EEU and FEV1 will be monitored every 30 minutes. During this 6-hour monitoring period, a LAR can appear with a drop in FEV1 of 15% and will be treated with short-acting  $\beta$ 2 agonist and corticosteroids if necessary. Approximately at the end of the 6-hour monitoring period, patients will undergo a physical exam and vital signs, including spirometry, and will be discharged home if there are no abnormal findings and if FEV1  $\geq 90\%$  of baseline. If FEV1 is  $< 90\%$  of the baseline value, patients will continue to be monitored at the clinic until the patient meets criteria for discharge. FEV1 will be monitored at home for approximately 18 hours after leaving the clinical unit (a total of 24 hours of monitoring from the end of the EEU exposure). If there is a 30% drop in FEV1 during home monitoring, the investigator(s) will receive an alarm by email to inform about the change in spirometry and the patient will be contacted and evaluated by a medical doctor.

Severe bronchoconstriction will be treated with oxygen, short-acting  $\beta$ 2 agonist by nebulization, and oral systemic corticosteroids.

Under the extremely rare circumstance that patients experience a severe systemic reaction to the EEU (anaphylaxis), with arterial hypotension, angioedema, or urticaria, patients will be treated with adrenaline 0.3 mg IM and will be transferred to the hospital emergency room, which is located within a 5-minute walk of the clinical trial unit.

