## **7.8. Concomitant Medications**

Any treatment administered from the time of informed consent to the end of the treatment final study visit will be considered concomitant medication. This includes medications that were started before the study and are ongoing during the study. This excludes all rescue treatment kit medications, taken at home within 24 hours from the EEU exposure. Rescue medications taken from the kit within 24 hours of EEU exposure will be collected separately.

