### **7.8.2. Permitted Medications**

Use of standard-of-care medications not listed as prohibited will be allowed. Treatment for acute reactions is allowed during the study (See Section [7.4](#)).

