5.4. Rescue/ Prohibited Medications

Rescue and prohibited medications will be based on both the efficacy and safety population.

The number and proportion of patients taking rescue medications at EEU exit, during the 6-hour observation period on-site and during the at-home monitoring period will be summarized for each treatment group and by type of rescue medication. The total dose of each rescue medication taken per patient will be calculated at each visit at EEU exit, during the 6-hour observation period on-site and during the at-home monitoring period, and will be summarized for each treatment group.

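### The SAP's prohibited-medication list copies the LAR-only steroid exemption but not the protocol's general permission for acute-reaction treatment, so on the SAP's wording steroids given on site for a severe EAR exclude the patient from the per-protocol set

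*SAP*

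**What the plan says.** Five places bear on this point.

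- **Protocol 7.4**, under a heading that covers both the EAR and the late asthmatic response (LAR), says severe bronchoconstriction will be treated with oxygen and a short-acting "agonist by nebulization, and oral systemic corticosteroids". It does not limit this to a LAR.
- **Protocol 7.8.1(f)** and **SAP 4.4(f)** list "Systemic steroid treatment (8 weeks prior to screening and during the study") as prohibited. A note in both gives one exemption: "systemic steroid treatment is allowed if clinically indicated for a LAR treatment after exposure to cat allergen in the EEU".
- **Protocol 7.8.2**, directly after the protocol's list, says "Treatment for acute reactions is allowed during the study" and refers to Section 7.4. The SAP has no counterpart.
- **SAP 4.4.1** repeats much of Protocol 7.4 but not its sentence on severe bronchoconstriction. For treatment on site it mentions corticosteroids only for a LAR.
- **SAP 3.2** lists among its criteria for a major protocol deviation "Had taken any prohibited medication during the double-blind phase". It also gives a general definition: "A major protocol violation is one that may affect the interpretation of study efficacy results".

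The SAP 10.1 summary table names both the FAS and the PPS as populations for time to EAR on Day 8 and on Days 29, 57 and 85.

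**The concern.** A per-protocol set is meant to remove departures from the protocol that could distort the efficacy result. Here the SAP's wording would remove a patient for receiving the treatment that Protocol 7.4 directs, and the reason for that treatment is the primary event in a severe form. Patients without an EAR cannot leave by this route. PPS membership would then be selected on the outcome that the PPS analysis is meant to check.

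For the challenge that prompted the treatment, the exclusion also has no methodological purpose. The EAR time is fixed before the steroid is given. Carryover into later challenges is a separate matter, and SAP 5.6.1 already explores it with a medication covariate. The criterion applies to the patient over the whole double-blind phase, so on its wording a steroid given after a later challenge could also remove that patient's Day 8 data.

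**Working it through.** **Classifying one case.** Take a patient with a severe EAR on Day 8 who receives oral corticosteroids in the observation room.

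| Source | Status of the steroid |
|---|---|
| Protocol 7.4 | Directed |
| Protocol 7.8.1(f) alone | Prohibited (not for a LAR) |
| Protocol 7.8.2 | Allowed as acute-reaction treatment |
| SAP 4.4(f) | Prohibited (not for a LAR) |
| SAP 4.3 | Concomitant medication (only kit drugs taken at home within 24 h are excepted) |
| SAP 3.2 | Major deviation, so out of the PPS |

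The protocol read as a whole permits the treatment. The SAP read by itself does not, and the SAP defines the PPS.

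**Scale, for illustration only.** The documents give no figure on this point. The planning model is used to see how large an effect could be.

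*Inputs.* Median time to EAR 58 and 132 minutes, censoring at 240 minutes, and 60 patients less 8 dropouts, so 26 per arm (Protocol 10.2, SAP 2.2 and 4.5.1). Exponential times are an assumption.

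*Check of the model against the plan's power.*
- EAR by 4 h on placebo: 1 − 0.5^(240/58) = 94.3%.
- EAR by 4 h on drug: 1 − 0.5^(240/132) = 71.6%.
- Difference: 22.7 points.
- Expected events: 26 × (0.943 + 0.716) = 43.2 (unrounded rates).
- Hazard ratio: 58/132 = 0.439.
- Schoenfeld power, one-sided 0.05: Φ(|ln 0.439| × √43.2 / 2 − 1.645) = 85.5%, close to the stated 84%.

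*Effect of removing a share s of the EARs.* An arm with EAR proportion p becomes p(1 − s)/(1 − ps), and 26ps patients leave. The share s is assumed.

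| s, placebo | s, drug | Patients removed (placebo, drug) | EAR by 4 h (placebo, drug) | Difference |
|---|---|---|---|---|
| 0% | 0% | 0, 0 | 94.3%, 71.6% | 22.7 points |
| 5% | 5% | 1.2, 0.9 | 94.0%, 70.6% | 23.4 points |
| 10% | 10% | 2.5, 1.9 | 93.7%, 69.5% | 24.3 points |
| 14% | 14% | 3.4, 2.6 | 93.5%, 68.5% | 25.0 points |
| 14% | 0% | 3.4, 0 | 93.5%, 71.6% | 21.8 points |

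With equal shares, the large-sample Cox hazard ratio moves from 0.439 to 0.434 at 5% and 0.427 at 10%.

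*Where 14% comes from.* In the validation study (Protocol 1), none of 20 cat-allergic patients needed more than a short-acting agonist. The one-sided 95% upper bound is 1 − 0.05^(1/20) = 13.9%. Only about half of those 20 had an EAR. Counted over 10 EAR patients, the bound is 1 − 0.05^(1/10) = 25.9%. At s = 26% in both arms about 6.4 placebo and 4.8 drug patients leave, and the hazard ratio is 0.405. These are bounds on a count of zero, not expected rates.

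*Direction.* With 14% removed on placebo, the difference returns to 22.7 points when about 4% of drug-arm EARs are removed. Below that share the PPS difference narrows, and above it the difference widens.

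**The case against.** The strongest reply is that the documents as a whole do not make this patient a violator. Protocol 7.8.2 permits treatment under 7.4. SAP 5.4 tabulates patients "taking rescue medications at EEU exit, during the 6-hour observation period on-site and during the at-home monitoring period". SAP 5.6.3 refers to steroid rescue medication within 24 hours of a challenge with no LAR limit. SAP 3.2 restricts major violations to those that may affect interpretation of efficacy, with membership settled before database lock. A careful team could therefore keep the patient.

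Much of this stands. A reader might infer that these patients must leave the PPS under the plan as a whole; Protocol 7.8.2 does not support that. The gap is still in the SAP's own text. The SAP 5.4 table and the FeNO model factor in SAP 5.6.3 do not say that such use is not prohibited. The general definition in SAP 3.2 is followed by a list that names any prohibited medication, with no exception for directed treatment.

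Three further inferences should not be drawn.

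- **That use of the home rescue kit is caught in the same way.** Protocol 7.8 defines concomitant medication and then says "This excludes all rescue treatment kit medications, taken at home within 24 hours from the EEU exposure". SAP 4.3 makes the same exception, and the SAP 4.4 list concerns concomitant medications. Home kit use within 24 hours is already outside it.
- **That the PPS would lean toward the drug.** This needs similar severe shares in the two arms. If the drug also lessens severity, the shift can go the other way, as the last row of the second table shows.
- **That steroids given at the screening cat challenge (visit 3) have the same consequence.** That treatment precedes the double-blind phase, so the PPS criterion does not reach it.

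**Conclusion.** The point holds as a defect in the SAP's wording. SAP 3.2 with 4.4 makes PPS membership depend on having a severe EAR treated on site with systemic steroids, although Protocol 7.8.2 permits that treatment.

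The reach is limited. The FAS is the primary set, so the primary estimate, test and power do not change. Only the PPS analyses of time to EAR are exposed. The size and direction of any bias cannot be stated. The documents give no severe-EAR rate, the one relevant count is 0 of 20, and at a zero rate nothing changes. The illustrative shifts rest on exponential times and assumed shares. The point merits correction because the rule selects on the outcome and removing it costs very little.

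**What to change.** 1. Reconcile Protocol 7.4, 7.8.1(f) and 7.8.2 with SAP 3.2 and 4.4, so that all give one rule on systemic steroids after a challenge. Which clinical rule applies is for the sponsor.
2. Add a sentence to SAP 3.2 or 4.4: medication given for a challenge-induced acute reaction under Protocol 7.4 is not by itself a reason for exclusion from the PPS. It stays in the SAP 5.4 rescue-medication tabulation, which already covers EEU exit, on-site and home use.
3. Make the change before any unblinding. That includes the optional first-step analysis after the last Day 8 challenge, which SAP 7 makes final for the primary endpoint.

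The cost is one SAP sentence and aligned protocol wording. No data collection or primary analysis changes.
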